9.6.3 Summaries of Baseline Characteristics

The comparability of the vaccination groups for each relevant demographic and baseline characteristic will be assessed using summary tables. No statistical hypothesis tests will be performed on these characteristics. The number and percentage of participants screened and randomized and the primary reasons for screening failure and discontinuation will be displayed. Demographic variables (eg, age, race, gender, birth weight, and gestational age), baseline characteristics, and prior and concomitant vaccinations and therapies will be summarized by vaccination group either by descriptive statistics or categorical tables.

9.7 Interim Analyses

A periodic review of safety and tolerability data across the V114 Phase 3 pediatric program will be conducted by an independent, unblinded, external DMC. A description of the structure and function of the DMC, along with the timing and content of the safety review will be outlined in the DMC charter. Information regarding the composition of the DMC is provided in Appendix 1. There are no plans to conduct an interim analysis of unblinded immunogenicity data in this study. However, unblinded immunogenicity data will be made available to the DMC upon request to enable a benefit-risk assessment.

The DMC will serve as the primary reviewer of the results of ongoing safety reviews and will make recommendations for discontinuation of the study or protocol modifications to an executive committee of the Sponsor (see Appendix 1 for details on the Committees Structure

for this study). If the DMC recommends modifications to the design of the protocol or discontinuation of the study, this Executive Oversight Committee (EOC) of the Sponsor (and potentially other limited Sponsor personnel) may be unblinded to results at the intervention level to act on these recommendations. The extent to which individuals are unblinded with respect to ongoing safety reviews will be documented by the external unblinded statistician. Additional logistical details will be provided in the DMC charter.

Study enrollment is likely to be ongoing at the time of external DMC review. Blinding to intervention assignment will be maintained at all investigational sites. Participant--level unblinding will be restricted to an external unblinded statistician performing ongoing safety reviews. Intervention-level ongoing safety reviews will be provided by the external unblinded statistician to the DMC. Prior to final study unblinding, the external unblinded statistician will not be involved in any discussions regarding modifications to the protocol, statistical methods, identification of protocol deviations, or data validation efforts after the safety reviews.

9.8 Multiplicity

The study will be considered to have met its primary immunogenicity objective if non-inferiority is demonstrated with respect to IgG GMCs and response rates for the 13 shared serotypes and superiority is demonstrated respect to IgG GMCs and response rates for the 2 unique serotypes at 30 days PD3. All hypotheses will be tested individually for each serotype at a 1-sided 0.025 alpha level. This approach controls the 1-sided type--I error rate at 0.025, thus no multiplicity adjustment is required. The study will be considered to have met its secondary objective for a specific concomitant vaccine if non-inferiority is demonstrated for all the antigens included in that concomitant vaccine.

No multiplicity adjustments will be made for the safety comparisons.

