
Objective: To compare anti-PnPs serotype-specific IgG geometric mean concentrations (GMCs) at 30 days following Dose 3 for participants administered V114 versus participants administered Prevenar 13TM. 
Hypothesis (H3): V114 is noninferior to Prevenar 13TM for the 13 shared serotypes between V114 and Prevenar 13TM based on anti-PnPs serotype-specific IgG GMCs at 30 days following Dose 3.
 
(The statistical criterion for non-inferiority requires the lower bound of the 2-sided 95% CI for anti-PnPs serotype-specific IgG GMC ratio [V114/ Prevenar 13TM] to be greater than 0.5).
 
Hypothesis (H4): V114 is superior to Prevenar 13TM for the 2 serotypes unique to V114 based on anti-PnPs serotype-specific IgG GMCs at 30 days following Dose 3.
 
(The statistical criterion for superiority requires the lower bound of the 2-sided 95% CI for anti-PnPs serotype-specific IgG GMC ratio [V114/ Prevenar 13TM] to be greater than 2.0).
	
Anti-PnPs serotype-specific IgG responses for the 15 serotypes contained in V114 at 30 days PD3

Objectives	Endpoints
Secondary	

 Objective: To compare the antigen-specific response rate to each antigen included in Vaxelis™ at 30 days following Dose 3 for participants administered V114 concomitantly with Vaxelis™ versus participants administered Prevenar 13™ concomitantly with Vaxelis™. 
Hypothesis (H5): Vaxelis™ administered concomitantly with V114 is non-inferior to Vaxelis™ administered concomitantly with Prevenar 13™ at 30 days following Dose 3 for each antigen included in Vaxelis™.
	
Antibody responses to:
 
 diphtheria toxoid tetanus toxoid pertussis toxin (PT) pertussis filamentous hemagglutinin (FHA) pertussis fimbriae 2/3 (FIM 2/3) pertussis pertactin (PRN) Haemophilus influenzae type b polyribosylribitol phosphate (Hib-PRP) hepatitis B surface antigen (HBsAg) poliovirus serotypes 1, 2, and 3 
at 30 days PD3 of V114 or Prevenar 13™

 Objective: To evaluate the anti-PnPs serotype-specific- IgG response rates and GMCs at 30 days following Dose 2 by each vaccination group. 	
 Anti-PnP serotype-specific IgG responses for the 15 serotypes contained in V114 at 30 days PD2

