Statistical Methods for Key Immunogenicity	To address the primary immunogenicity non-inferiority/superiority objectives (H1 and H2), the comparison between groups will be made based on the proportion of anti-PnPs serotype-specific IgG $\geq 0.35 \mu\text{g/mL}$ for the 15 serotypes contained in V114 at 30 days PD3. The between-treatment difference (V114 minus Prevenar 13™) and its 95% CI will be calculated using the Miettinen and Nurminen (M&N) method [Miettinen, O. and Nurminen, M. 1985]. To address the primary immunogenicity non-inferiority/superiority objectives (H3 and H4), the comparison between groups will be made based on serotype-specific IgG GMCs for the 15 serotypes contained in V114 at 30 days PD3. The estimation of the IgG GMC ratios and computation of the corresponding 95% CIs will be calculated using the t-distribution with the variance estimate from a linear model utilizing the log-transformed antibody concentration as the response and a single term for vaccination group.

	
To address the secondary objectives regarding the non-inferiority evaluation of concomitant antigens contained in Vaxelis™ at 30 days PD3, the comparison between groups will be made based on the proportion of participants achieving the antigen-specific antibody threshold value described in Section 9.9.1. The between-treatment difference (V114 minus Prevenar 13™) and the corresponding 95% CIs will be calculated using the M&N method [Miettinen, O. and Nurminen, M. 1985].
 
All hypothesis testing, including both non-inferiority and superiority, will be based on the lower bound of the 2-sided 95% CI to be greater than the prespecified margins listed in Section 9.9.1.

Statistical Methods for Key Safety Analyses	The analysis of safety results will follow a tiered approach. p--values (Tier 1 endpoints) and 95% CIs (Tier 1 and Tier 2 endpoints) will be provided for between-vaccination group differences in the percentage of participants with events; these analyses will be performed using the M&N method [Miettinen, O. and Nurminen, M. 1985].

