9.9 Sample Size and Power Calculations

9.9.1 Sample Size and Power for Immunogenicity Analyses

The study will randomize participants in a 1:1 ratio to the 2 vaccination groups. The overall sample size will be approximately 1180 with 590 participants into each vaccination group. The sample size was chosen to ensure sufficient power for the multiple endpoints across both primary and secondary hypotheses. It is assumed that approximately 472 participants per vaccination group will be evaluable for PP immunogenicity analyses at 30 days PD2 (based on an 80% evaluability rate), and approximately 443 participants per vaccination group will be evaluable for PP immunogenicity analyses at 30 days PD3 (based on a 75% evaluability rate).

With this study sample size and the assumptions listed below, the overall power for the primary hypotheses is >95% for demonstrating non-inferiority of V114 to Prevenar 13™ for the 13 shared serotypes and superiority for the 2 unique serotypes for V114 formulations. The overall power for the secondary hypotheses for concomitant antigens evaluation is ~90%. The power for individual hypothesis components is provided below.

For the primary immunogenicity endpoint/hypothesis (H1), the study has >95% power at a 1--sided 2.5% alpha level to demonstrate V114 is non-inferior to Prevenar 13TM at 30 days PD3 for anti-PnPs serotype-specific IgG responses at or above the threshold value of 0.35 µg/mL for the 13 shared serotypes between V114 and Prevenar 13TM based on the following assumptions: (1) an approximately 75% evaluability rate at PD3 as observed in previous Phase 2 V114 pediatric studies; (2) a non-inferiority margin of --0.1 for the difference (V114-Prevenar 13TM); and (3) underlying serotype-specific IgG response rates (proportion of participants meeting serotype-specific IgG threshold value of ≥ 0.35 µg/mL at 30 days PD3 of V114 or Prevenar 13TM) are 95% at 30 days PD3.

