For the primary immunogenicity endpoint/hypothesis (H2), the study has >95% power at a 1--sided 2.5% alpha level to demonstrate V114 is superior to Prevenar 13TM at 30 days PD3 for anti-PnPs serotype-specific IgG responses at or above the threshold value of 0.35 µg/mL for the 2 unique serotypes contained in V114 based on the following assumptions: (1) an approximately 75% evaluability rate at 30 days PD3 as observed in previous V114 pediatric Phase 2 studies; (2) a superiority margin of 0.1 for the difference (V114-Prevenar 13TM); and (3) underlying serotype-specific IgG response rates (proportion of participants meeting serotype-specific IgG threshold value of ≥ 0.35 µg/mL at 30 days PD3 of V114 or Prevenar 13TM) are 95% in V114 group and 2% in Prevenar 13TM group at 30 days PD3.

For the primary immunogenicity endpoint/hypothesis (H3), the study has >95% power at a 1--sided 2.5% alpha level to demonstrate V114 is non-inferior to Prevenar 13TM at 30 days PD3 for anti-PnPs serotype-specific IgG GMCs at 30 days PD3 based on the following assumptions: (1) an approximately 75% evaluability rate at 30 days PD3 as observed in previous V114 pediatric Phase 2 studies; (2) a non-inferiority margin of 0.5 (V114/Prevenar 13TM); (3) SD of anti-PnPs serotype-specific IgG GMCs in log scale is 1.1 as those observed in previous MSD studies, and (4) the true GMC ratio (V114/Prevenar 13TM) for anti-PnPs serotype-specific IgG GMCs is 1.0.

For the primary immunogenicity endpoint/hypothesis (H4), the study has >95% power at a 1-sided 2.5% alpha level to demonstrate V114 is superiority to Prevenar 13TM at 30 days PD3 for anti-PnPs serotype-specific IgG GMCs for the 2 unique serotypes contained in V114 based on the following assumptions: (1) an approximately 75% evaluability rate at PD3 as observed in previous Phase 2 V114 pediatric studies; (2) a superiority margin of 2.0 (V114/Prevenar 13TM); and (3) SD of anti-PnPs serotype-specific IgG GMCs in log scale is 1.1 as those observed in previous MSD studies, and (4) the true GMC ratio (V114/Prevenar 13TM) for anti-PnPs serotype-specific IgG GMCs is 10.0.

The study is considered to have met its primary objective if V114 is non-inferior to Prevenar 13TM for the 13 shared serotypes and superior to Prevenar 13TM for the 2 unique serotypes contained in V114.

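### Does testing H5 at full 1-sided 0.025, with no gate on the primary objective, break the type I error control stated in Section 9.8?

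*Combined protocol and SAP*

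**What the plan says.** Section 9.8 first defines primary success: non-inferiority on both IgG measures for the 13 shared serotypes and superiority on both for the 2 unique ones. It then says "All hypotheses will be tested individually for each serotype at a 1-sided 0.025 alpha level" and draws the conclusion "This approach controls the 1-sided type--I error rate at 0.025, thus no multiplicity adjustment is required". Only after that does it turn to the concomitant vaccine: "The study will be considered to have met its secondary objective for a specific concomitant vaccine if non-inferiority is demonstrated for all the antigens" it contains. The summary in Section 9.1 keeps the same order.

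H5 is a formal hypothesis. Section 3 states it ("Hypothesis (H5): Vaxelis™ administered concomitantly with V114 is non-inferior to Vaxelis™" given with the comparator), Section 9.6.1 gives its null and alternative, and Table 8 lists 11 antigens with margins and a joint power of 90.9%. Its test level comes from Section 9.1: "All hypothesis testing, including both non-inferiority and superiority, will be based on the lower bound of the 2-sided 95% CI" exceeding the margin, which is 1-sided 0.025.

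No section makes H5 depend on H1–H4, orders the two objectives or splits alpha between them. Nor does any section say that 0.025 covers primary and secondary hypotheses together.

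**The concern.** An all-must-pass rule controls error within one objective. It does nothing across two objectives that can be declared met independently of each other. H5 has the features of a confirmatory claim. The opening of Section 9 requires a protocol amendment for changes to primary or key secondary hypotheses and treats non-confirmatory analyses differently, and Section 9.9.1 sizes the trial for both sets of hypotheses.

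Section 9.8 refers to all hypotheses and says that no adjustment is needed, without limiting either statement to H1–H4. A reader could take 0.025 as the error rate for the whole set of formal claims. On that reading the figure would be wrong by almost a factor of two, and a Vaxelis claim could be made at full alpha after the primary objective had failed.

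**Working it through.** **Inputs.** Per-comparison level: 1-sided 0.025 (Sections 9.1, 9.8). Evaluable at 30 days after Dose 3: 443 per group, 75% of 590 (Section 9.9.1). H5 (Table 8): 2 antigens at 95% with margin −10%, 4 at 97% with −5%, 5 at 90% with −10%. Primary (Section 9.9.1): response rates 95% in both groups with margin −0.1 (H1); 95% against 2% with margin 0.1 (H2); log-scale SD 1.1, true ratio 1.0 with margin 0.5 (H3), and 10.0 with margin 2.0 (H4).

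**1. The stated 0.025, primary objective.** Primary success needs 13 + 2 + 13 + 2 = 30 passes. If the objective is false, at least one comparison is truly at or beyond its margin, and false success requires that one to pass. Hence P(false success) ≤ 0.025. The stated figure is reproduced with no adjustment.

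**2. The same argument for H5.** All 11 antigens must pass, so a false H5 claim has probability at most 0.025. A false H5 claim made after primary failure is a subset of that event, so it is also at most 0.025. The M&N interval is asymptotic. Its exact size at n = 443 is 0.0233 for 92% against 97% (margin −5%) and 0.0242 for 85% against 95% (margin −10%), both below nominal.

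**3. Both objectives together, no gate.**
- Any dependence: at most 0.025 + 0.025 = 0.050.
- Independent, one comparison at its margin in each objective and the rest certain to pass: 1 − 0.975² = 1 − 0.950625 = 0.0494.
- Independent, the rest at the plan's assumed rates: the primary contributes 0.0250 and H5 contributes 0.025 × 0.909/0.9787 = 0.0232, so 1 − (0.9750)(0.9768) = 0.0476.
- Positive correlation between the two margin comparisons (an assumption; the documents give none): 0.0476 at 0.3, 0.0454 at 0.5, 0.0417 at 0.7, 0.0352 at 0.9. Both objectives use the same infants, so some positive correlation is plausible.

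**4. Power.** With the Farrington–Manning variance, per-antigen powers at n = 443 are 1.000, 0.9787 and 0.9980. Their product is 1.000² × 0.9787⁴ × 0.9980⁵ = 0.908, against the stated 90.9%. Exact enumeration of the M&N test gives 0.928. For the primary objective, H1 over 13 serotypes gives 0.99994. For H3, ln 2 / (1.1 × √(2/443)) = 0.693/0.0739 = 9.38, far above 1.96; H2 and H4 are further out still. The joint product is 0.9999, consistent with the stated >95%.

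**5. What other rules would do.**

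| Rule | Error across both | H5 power |
|---|---|---|
| As planned | ≤ 5.0% | 90.9% |
| H5 only after primary success | ≤ 2.5% | 0.909 × 0.9999 = 90.9% |
| Same gate, primary power only 95% | ≤ 2.5% | 0.909 × 0.95 = 86.4% if independent; at least 0.909 + 0.95 − 1 = 85.9% |
| 0.0125 for each objective | ≤ 2.5% | 81.0% |

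**The case for a change.** The strongest case for a change is that the gate takes one sentence, costs almost nothing on the plan's assumptions and makes 0.025 true on any reading. Section 9.8 expressly says that the safety comparisons are unadjusted but says nothing comparable for H5, so a reader could believe H5 is covered. These points stand as facts: the scope of the sentence is not spelled out, there is no gate, and the joint ceiling is 4.94% to 5.0%.

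They do not amount to an error. The sentence follows the primary rule and the reference to serotypes, and precedes the rule for antigens, so its natural subject is the primary objective. The feared harm, an uncontrolled Vaxelis claim after primary failure, does not arise, because H5 carries its own 2.5% limit.

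The low cost of the gate also depends on favourable assumptions: 95% response in both groups for every shared serotype and a true GMC ratio of 1.0. Section 10.7.1.1 reports that an earlier formulation gave infants lower responses than the comparator for some shared serotypes, although it also reports better performance with Formulation B. The gate would bite when those assumptions fail. A single missed serotype says little about whether V114 interferes with Vaxelis, yet it would reduce H5 to description. Adding the gate would also need a protocol amendment under the opening of Section 9.

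**Conclusion.** The concern does not call for a change. Section 9.8's 0.025 is exact for the primary objective, and H5 is separately held to at most 0.025. What the plan leaves open is the chance of at least one false success across the two objectives: at most 5.0%, 4.94% in the independent worst case, 4.76% with the other comparisons at the plan's assumed rates, and lower with positive correlation. Reaching the ceiling needs one comparison in each objective exactly at its margin and nearly all others sure to pass.

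Controlling error per objective is coherent here: H5 asks a distinct question, is labelled secondary, and plays no part in primary success. Gating would exchange a lower joint error rate for the loss of a valid H5 conclusion whenever any of 30 primary comparisons fails, which is a trade-off and not a correction. Spelling out that 0.025 applies to each objective separately would add clarity but alter no test, interval or decision. An analyst following the text would report the two objectives side by side, each at its own level, without claiming joint control.

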9.9 Sample Size and Power Calculations

9.9.1 Sample Size and Power for Immunogenicity Analyses

The study will randomize participants in a 1:1 ratio to the 2 vaccination groups. The overall sample size will be approximately 1180 with 590 participants into each vaccination group. The sample size was chosen to ensure sufficient power for the multiple endpoints across both primary and secondary hypotheses. It is assumed that approximately 472 participants per vaccination group will be evaluable for PP immunogenicity analyses at 30 days PD2 (based on an 80% evaluability rate), and approximately 443 participants per vaccination group will be evaluable for PP immunogenicity analyses at 30 days PD3 (based on a 75% evaluability rate).

With this study sample size and the assumptions listed below, the overall power for the primary hypotheses is >95% for demonstrating non-inferiority of V114 to Prevenar 13™ for the 13 shared serotypes and superiority for the 2 unique serotypes for V114 formulations. The overall power for the secondary hypotheses for concomitant antigens evaluation is ~90%. The power for individual hypothesis components is provided below.

For the primary immunogenicity endpoint/hypothesis (H1), the study has >95% power at a 1--sided 2.5% alpha level to demonstrate V114 is non-inferior to Prevenar 13TM at 30 days PD3 for anti-PnPs serotype-specific IgG responses at or above the threshold value of 0.35 µg/mL for the 13 shared serotypes between V114 and Prevenar 13TM based on the following assumptions: (1) an approximately 75% evaluability rate at PD3 as observed in previous Phase 2 V114 pediatric studies; (2) a non-inferiority margin of --0.1 for the difference (V114-Prevenar 13TM); and (3) underlying serotype-specific IgG response rates (proportion of participants meeting serotype-specific IgG threshold value of ≥ 0.35 µg/mL at 30 days PD3 of V114 or Prevenar 13TM) are 95% at 30 days PD3.

For the primary immunogenicity endpoint/hypothesis (H2), the study has >95% power at a 1--sided 2.5% alpha level to demonstrate V114 is superior to Prevenar 13TM at 30 days PD3 for anti-PnPs serotype-specific IgG responses at or above the threshold value of 0.35 µg/mL for the 2 unique serotypes contained in V114 based on the following assumptions: (1) an approximately 75% evaluability rate at 30 days PD3 as observed in previous V114 pediatric Phase 2 studies; (2) a superiority margin of 0.1 for the difference (V114-Prevenar 13TM); and (3) underlying serotype-specific IgG response rates (proportion of participants meeting serotype-specific IgG threshold value of ≥ 0.35 µg/mL at 30 days PD3 of V114 or Prevenar 13TM) are 95% in V114 group and 2% in Prevenar 13TM group at 30 days PD3.

For the primary immunogenicity endpoint/hypothesis (H3), the study has >95% power at a 1--sided 2.5% alpha level to demonstrate V114 is non-inferior to Prevenar 13TM at 30 days PD3 for anti-PnPs serotype-specific IgG GMCs at 30 days PD3 based on the following assumptions: (1) an approximately 75% evaluability rate at 30 days PD3 as observed in previous V114 pediatric Phase 2 studies; (2) a non-inferiority margin of 0.5 (V114/Prevenar 13TM); (3) SD of anti-PnPs serotype-specific IgG GMCs in log scale is 1.1 as those observed in previous MSD studies, and (4) the true GMC ratio (V114/Prevenar 13TM) for anti-PnPs serotype-specific IgG GMCs is 1.0.

For the primary immunogenicity endpoint/hypothesis (H4), the study has >95% power at a 1-sided 2.5% alpha level to demonstrate V114 is superiority to Prevenar 13TM at 30 days PD3 for anti-PnPs serotype-specific IgG GMCs for the 2 unique serotypes contained in V114 based on the following assumptions: (1) an approximately 75% evaluability rate at PD3 as observed in previous Phase 2 V114 pediatric studies; (2) a superiority margin of 2.0 (V114/Prevenar 13TM); and (3) SD of anti-PnPs serotype-specific IgG GMCs in log scale is 1.1 as those observed in previous MSD studies, and (4) the true GMC ratio (V114/Prevenar 13TM) for anti-PnPs serotype-specific IgG GMCs is 10.0.

The study is considered to have met its primary objective if V114 is non-inferior to Prevenar 13TM for the 13 shared serotypes and superior to Prevenar 13TM for the 2 unique serotypes contained in V114.

For the secondary immunogenicity endpoint/hypothesis (H5), the power is ~90.9% the non-inferiority hypotheses when VaxelisTM administered concomitantly with V114 or Prevenar 13TM, respectively. This is based on the assumptions of approximately 75% evaluability rate at PD3 for VaxelisTM. The assumed response rates, GMT, and non-inferiority margins are listed in [Table 8](#).

Table 8 Summary of Endpoints and Power for Concomitant Vaccine Antigens

	Antigen	Endpoint	Time point	Assumed Response Rate or Standard Deviation	NI Margin	Power
Vaxelis™	Diphtheria toxoid	% \geq 0.1 IU/mL	PD3	95%	-10%	90.9%
	Tetanus toxoid	% \geq 0.1 IU/mL	PD3	97%	-5%	
	Pertussis – PT	% \geq 5 EU/mL	PD3	90%	-10%	
	Pertussis – FHA	% \geq 5 EU/mL	PD3	90%	-10%	
	Pertussis – FIM 2/3	% \geq 20 EU/mL	PD3	90%	-10%	
	Pertussis – PRN	% \geq 5 EU/mL	PD3	90%	-10%	
	Hib-PRP	% \geq 0.15 μ g/mL	PD3	90%	-10%	
	HBsAg	% \geq 10 mIU/mL	PD3	95%	-10%	
	Poliovirus 1	% with Nab \geq 1:8 dilution	PD3	97%	-5%	
	Poliovirus 2	% with Nab \geq 1:8 dilution	PD3	97%	-5%	
	Poliovirus 3	% with Nab \geq 1:8 dilution	PD3	97%	-5%	

EU = endotoxin unit; FHA = filamentous hemagglutinin; FIM 2/3 = fimbriae types 2 and 3; HBsAg = hepatitis B surface antigen; Hib= *Haemophilus influenzae* type b; IU = international unit; Nab = neutralizing antibodies; NI = non-inferiority; PD = postdose; PRN = pertactin; PRP = polyribosylribitol phosphate; PT = pertussis toxin; SD = standard deviation (in log scale).

